**Table 168: Laboratory Summary Statistics by Time Point and Treatment Group for the Safety Population – APTT (sec)**

[Implementation Note: Repeat for the following treatment groups: SAR440894 0.3 mg/kg, SAR440894 1 mg/kg, SAR440894 3 mg/kg, SAR440894 10 mg/kg, SAR440894 20 mg/kg, Placebo.]

The table will include the following time points: Baseline, Day 2, Day 3, Day 4, Day 7, Day 14, Day 28, Day 56, Day 84, Day 112, Final Visit (Day 150).]

Time Point	Treatment Group	Value at Visit					Change from Baseline				
		n	Mean	SD	Median	Min, Max	n	Mean	SD	Median	Min, Max
Baseline	SAR440894 0.3 mg/kg (N = X)	x	xx.x	xx.x	xx.x	xx.x, xx.x	-	-	-	-	-
	...						-	-	-	-	-
	Placebo (N = X)						-	-	-	-	-
Day 2	SAR440894 0.3 mg/kg (N = X)						x	xx.x	xx.x	xx.x	xx.x, xx.x
	...										
	Placebo (N = X)										
...	...										

Notes: N = Number of participants in the Safety population. n = Number of participants with a non-missing lab value at the respective visit. For the change from baseline, n represents the number of participants with non-missing values at baseline and the respective visit. SD = Standard Deviation. Min = Minimum. Max = Maximum.

**Tables with Similar Format:****Table 169: Laboratory Summary Statistics by Time Point and Treatment Group for the Safety Population – Prothrombin Time (sec)**

[Implementation Note: Generate one table for each chemistry parameter. For calculated fields (Mean, SD, Median), decimal place should be the format in which the data were collected + 1 extra place. For Min, Max, decimal place should be in the same format in which the data were collected.]

[Repeat for each Chemistry Laboratory Parameter, number each table separately]

**Table 170: Laboratory Summary Statistics by Time Point and Treatment Group for the Safety Population – INR (Ratio)**

**Table 171: Clinically Significant Graded Coagulation Results by Maximum Severity Post-Baseline, Parameter, and Treatment Group for Participants in the Safety Population Enrolled Prior to Protocol v11.0**

[Implementation Note: Repeat for the following treatment groups: All Participants, SAR440894 0.3 mg/kg, SAR440894 1 mg/kg, SAR440894 3 mg/kg, SAR440894 10 mg/kg, SAR440894 20 mg/kg, and Placebo.]

The table will include the following parameters: APTT, Prothrombin Time, and INR.]

Parameter	Treatment Group	N	Mild / Grade 1		Moderate/ Grade 2		Severe/ Grade 3	
			n	%	n	%	n	%
APTT	All Participants	x	x	xx	x	xx	x	xx
	SAR440894 0.3 mg/kg							
	...							
	Placebo							
Prothrombin Time	All Participants							
	SAR440894 0.3 mg/kg							
	...							
	Placebo							
INR	All Participants							
	SAR440894 0.3 mg/kg							
	...							
	Placebo							

Notes: Participants are counted once per maximum severity among all clinically significant labs experienced at any time point post baseline, including unscheduled assessments. N = Number of participants in the Safety Population enrolled prior to Protocol v11.0 with available results post-baseline.

**Table 172: Clinically Significant Graded Coagulation Results by Maximum Severity Post-Baseline, Parameter, and Treatment Group for Participants in the Safety Population Enrolled Under Protocol v11.0**

[Implementation Note: Repeat for the following treatment groups: All Participants, SAR440894 0.3 mg/kg, SAR440894 1 mg/kg, SAR440894 3 mg/kg, SAR440894 10 mg/kg, SAR440894 20 mg/kg, and Placebo.

The table will include the following parameters: APTT, Prothrombin Time, and INR.]

Parameter	Treatment Group	N	Mild / Grade 1		Moderate/ Grade 2		Severe/ Grade 3		Life-threatening/ Grade 4		Death/ Grade 5	
			n	%	n	%	n	%	n	%	n	%
APTT	All Participants	x	x	xx	x	xx	x	xx	x	xx	x	xx
	SAR440894 0.3 mg/kg											
	...											
	Placebo											
Prothrombin Time	All Participants											
	SAR440894 0.3 mg/kg											
	...											
	Placebo											
INR	All Participants											
	SAR440894 0.3 mg/kg											
	...											
	Placebo											
...	...											

Notes: Participants are counted once per maximum severity among all clinically significant labs experienced at any time point post baseline, including unscheduled assessments. N = Number of participants in the Safety Population enrolled under Protocol v11.0 with available results post-baseline.

#### 14.3.5.4 Urinalysis Results

**Table 173: Laboratory Results by Severity, Time Point, and Treatment Group for Participants in the Safety Population Enrolled Prior to Protocol v11.0 – Any Urinalysis Parameter**

[Implementation Note: Repeat for the following treatment groups: All Participants, SAR440894 0.3 mg/kg, SAR440894 1 mg/kg, SAR440894 3 mg/kg, SAR440894 10 mg/kg, SAR440894 20 mg/kg, Placebo.]

The table will include the following time points: Baseline, Day 2, Day 3, Day 4, Day 7, Day 14, Day 28, Day 56, Day 84, Day 112, Final Visit (Day 150), Max Severity Post Baseline.]

Time Point	Treatment Group	Baseline Severity	Post-Baseline Severity					
			None		Mild / Grade 1		Moderate/ Grade 2	
			n	%	n	%	n	%
Day 2	All Participants (N=X)	None						
		Mild						
	SAR440894 0.3 mg/kg (N=X)	None						
		Mild						
	...	...						
		...						
	Placebo (N=X)	None						
		Mild						
...	...	...						
Max Severity Post Baseline	All Participants (N=X)	None						
		Mild						
	SAR440894 0.3 mg/kg (N=X)	None						
		Mild						
	...	...						
		...						

**Table 173: Laboratory Results by Severity, Time Point, and Treatment Group for Participants in the Safety Population Enrolled Prior to Protocol v11.0 – Any Urinalysis Parameter (continued)**

Time Point	Treatment Group	Baseline Severity	Post-Baseline Severity							
			None		Mild / Grade 1		Moderate/ Grade 2		Severe/ Grade 3	
			n	%	n	%	n	%	n	%
Placebo (N=X)	None									
		Mild								

Notes: The “Max Post Baseline” rows indicate the maximum severity experienced by each participant at any time point post baseline, including unscheduled assessments. N = Number of participants in the Safety Population enrolled prior to Protocol v11.0 with non-missing results at the given time point.

**Table 174: Laboratory Results by Severity, Time Point, and Treatment Group for Participants in the Safety Population Enrolled Under Protocol v11.0 – Any Urinalysis Parameter**

[Implementation Note: Repeat for the following treatment groups: All Participants, SAR440894 0.3 mg/kg, SAR440894 1 mg/kg, SAR440894 3 mg/kg, SAR440894 10 mg/kg, SAR440894 20 mg/kg, Placebo.

The table will include the following time points: Baseline, Day 2, Day 3, Day 4, Day 7, Day 14, Day 28, Day 56, Day 84, Day 112, Final Visit (Day 150), Max Severity Post Baseline.]

Time Point	Treatment Group	Baseline Severity	Post-Baseline Severity											
			None		Mild / Grade 1		Moderate/ Grade 2		Severe/ Grade 3		Life-threatening/ Grade 4		Death/ Grade 5	
			n	%	n	%	n	%	n	%	n	%	n	%
Day 2	All Participants (N=X)	None												
		Mild												
	SAR440894 0.3 mg/kg (N=X)	None												
		Mild												
	...	...												
		...												
	Placebo (N=X)	None												
		Mild												
...	...	...												
Max Severity Post Baseline	All Participants (N=X)	None												
		Mild												
	SAR440894 0.3 mg/kg (N=X)	None												
		Mild												
	...	...												
		...												
	Placebo (N=X)	None												
		Mild												

**Table 174: Laboratory Results by Severity, Time Point, and Treatment Group for Participants in the Safety Population Enrolled Under Protocol v11.0 – Any Urinalysis Parameter (continued)**

Time Point	Treatment Group	Baseline Severity	Post-Baseline Severity											
			None		Mild / Grade 1		Moderate/ Grade 2		Severe/ Grade 3		Life-threatening/ Grade 4		Death/ Grade 5	
			n	%	n	%	n	%	n	%	n	%	n	%
Notes: The “Max Post Baseline” rows indicate the maximum severity experienced by each participant at any time point post baseline, including unscheduled assessments. N = Number of participants in the Safety Population enrolled under Protocol v11.0 with non-missing results at the given time point.														

**Tables with Similar Format:****Table 175: Laboratory Results by Severity, Time Point, and Treatment Group for Participants in the Safety Population Enrolled Prior to Protocol v11.0 – Urine Protein**

[Implementation Note: This table will have similar format to Table 173.

If parameter is not graded, then only “Within Normal Range” and “Outside Normal Range” columns will be included, baseline severity will be either “None” or “ONR” and “ONR = Outside Normal Range.” Will be added to the footnote (see Table 191 as an example).]

**Table 176: Laboratory Results by Severity, Time Point, and Treatment Group for Participants in the Safety Population Enrolled Under Protocol v11.0 – Urine Protein**

[Implementation Note: This table will have similar format to Table 174.

If parameter is not graded, then only “Within Normal Range” and “Outside Normal Range” columns will be included, baseline severity will be either “None” or “ONR” and “ONR = Outside Normal Range.” Will be added to the footnote (see Table 192 as an example).]

**Table 177: Laboratory Results by Severity, Time Point, and Treatment Group for Participants in the Safety Population Enrolled Prior to Protocol v11.0 – Urine Glucose**

[Implementation Note: This table will have similar format to Table 173.

If parameter is not graded, then only “Within Normal Range” and “Outside Normal Range” columns will be included, baseline severity will be either “None” or “ONR” and “ONR = Outside Normal Range.” Will be added to the footnote (see Table 191 as an example).]

**Tables with Similar Format (continued):****Table 178: Laboratory Results by Severity, Time Point, and Treatment Group for Participants in the Safety Population Enrolled Under Protocol v11.0 – Urine Glucose**

[Implementation Note: This table will have similar format to Table 174.

If parameter is not graded, then only “Within Normal Range” and “Outside Normal Range” columns will be included, baseline severity will be either “None” or “ONR” and “ONR = Outside Normal Range.” Will be added to the footnote (see Table 192 as an example).]

**Table 179: Laboratory Results by Severity, Time Point, and Treatment Group for Participants in the Safety Population Enrolled Prior to Protocol v11.0 – Bilirubin**

[Implementation Note: This table will have similar format to Table 173.

If parameter is not graded, then only “Within Normal Range” and “Outside Normal Range” columns will be included, baseline severity will be either “None” or “ONR” and “ONR = Outside Normal Range.” Will be added to the footnote (see Table 191 as an example).]

**Table 180: Laboratory Results by Severity, Time Point, and Treatment Group for Participants in the Safety Population Enrolled Under Protocol v11.0 – Bilirubin**

[Implementation Note: This table will have similar format to Table 174.

If parameter is not graded, then only “Within Normal Range” and “Outside Normal Range” columns will be included, baseline severity will be either “None” or “ONR” and “ONR = Outside Normal Range.” Will be added to the footnote (see Table 192 as an example).]

**Table 181: Laboratory Results by Severity, Time Point, and Treatment Group for Participants in the Safety Population Enrolled Prior to Protocol v11.0 – Nitrite**

[Implementation Note: This table will have similar format to Table 173.

If parameter is not graded, then only “Within Normal Range” and “Outside Normal Range” columns will be included, baseline severity will be either “None” or “ONR” and “ONR = Outside Normal Range.” Will be added to the footnote (see Table 191 as an example).]

**Table 182: Laboratory Results by Severity, Time Point, and Treatment Group for Participants in the Safety Population Enrolled Under Protocol v11.0 – Nitrite**

[Implementation Note: This table will have similar format to Table 174.

If parameter is not graded, then only “Within Normal Range” and “Outside Normal Range” columns will be included, baseline severity will be either “None” or “ONR” and “ONR = Outside Normal Range.” Will be added to the footnote (see Table 192 as an example).]

**Tables with Similar Format (continued):****Table 183: Laboratory Results by Severity, Time Point, and Treatment Group for Participants in the Safety Population Enrolled Prior to Protocol v11.0 – Occult Blood**

[Implementation Note: This table will have similar format to Table 173.]

If parameter is not graded, then only “Within Normal Range” and “Outside Normal Range” columns will be included, baseline severity will be either “None” or “ONR” and “ONR = Outside Normal Range.” Will be added to the footnote (see Table 191 as an example).]

**Table 184: Laboratory Results by Severity, Time Point, and Treatment Group for Participants in the Safety Population Enrolled Under Protocol v11.0 – Occult Blood**

[Implementation Note: This table will have similar format to Table 174.]

If parameter is not graded, then only “Within Normal Range” and “Outside Normal Range” columns will be included, baseline severity will be either “None” or “ONR” and “ONR = Outside Normal Range.” Will be added to the footnote (see Table 192 as an example).]

**Table 185: Laboratory Results by Severity, Time Point, and Treatment Group for Participants in the Safety Population Enrolled Prior to Protocol v11.0 – Urine WBC**

[Implementation Note: This table will have similar format to Table 173.]

If parameter is not graded, then only “Within Normal Range” and “Outside Normal Range” columns will be included, baseline severity will be either “None” or “ONR” and “ONR = Outside Normal Range.” Will be added to the footnote (see Table 191 as an example).]

**Table 186: Laboratory Results by Severity, Time Point, and Treatment Group for Participants in the Safety Population Enrolled Under Protocol v11.0 – Urine WBC**

[Implementation Note: This table will have similar format to Table 174.]

If parameter is not graded, then only “Within Normal Range” and “Outside Normal Range” columns will be included, baseline severity will be either “None” or “ONR” and “ONR = Outside Normal Range.” Will be added to the footnote (see Table 192 as an example).]

**Table 187: Laboratory Results by Severity, Time Point, and Treatment Group for Participants in the Safety Population Enrolled Prior to Protocol v11.0 – Urine RBC**

[Implementation Note: This table will have similar format to Table 173.]

If parameter is not graded, then only “Within Normal Range” and “Outside Normal Range” columns will be included, baseline severity will be either “None” or “ONR” and “ONR = Outside Normal Range.” Will be added to the footnote (see Table 191 as an example).]

**Tables with Similar Format (continued):****Table 188: Laboratory Results by Severity, Time Point, and Treatment Group for Participants in the Safety Population Enrolled Under Protocol v11.0 – Urine RBC**

[Implementation Note: This table will have similar format to Table 174.

If parameter is not graded, then only “Within Normal Range” and “Outside Normal Range” columns will be included, baseline severity will be either “None” or “ONR” and “ONR = Outside Normal Range.” Will be added to the footnote (see Table 192 as an example).]

**Table 189: Laboratory Results by Severity, Time Point, and Treatment Group for Participants in the Safety Population Enrolled Prior to Protocol v11.0 – Urobilinogen**

[Implementation Note: This table will have similar format to Table 173.

If parameter is not graded, then only “Within Normal Range” and “Outside Normal Range” columns will be included, baseline severity will be either “None” or “ONR” and “ONR = Outside Normal Range.” Will be added to the footnote (see Table 191 as an example).]

**Table 190: Laboratory Results by Severity, Time Point, and Treatment Group for Participants in the Safety Population Enrolled Under Protocol v11.0 – Urobilinogen**

[Implementation Note: This table will have similar format to Table 174.

If parameter is not graded, then only “Within Normal Range” and “Outside Normal Range” columns will be included, baseline severity will be either “None” or “ONR” and “ONR = Outside Normal Range.” Will be added to the footnote (see Table 192 as an example).]

**Table 191: Laboratory Results by Severity, Time Point, and Treatment Group for Participants in the Safety Population Enrolled Prior to Protocol v11.0 – Ketones**

[Implementation Note: Repeat for the following treatment groups: All Participants, SAR440894 0.3 mg/kg, SAR440894 1 mg/kg, SAR440894 3 mg/kg, SAR440894 10 mg/kg, SAR440894 20 mg/kg, Placebo.]

The table will include the following time points: Baseline, Day 2, Day 3, Day 4, Day 7, Day 14, Day 28, Day 56, Day 84, Day 112, Final Visit (Day 150), Max Severity Post Baseline.]

Time Point	Treatment Group	Baseline Severity	Post-Baseline Severity			
			Within Normal Range		Outside Normal Range	
			n	%	n	%
Day 2	All Participants (N=X)	None	x	xx	x	xx
		ONR				
	SAR440894 0.3 mg/kg (N=X)	None				
		ONR				
	...	...				
		...				
	Placebo (N=X)	None				
		ONR				
...	...	...				
Max Severity Post Baseline	All Participants (N=X)	None				
		ONR				
	SAR440894 0.3 mg/kg (N=X)	None				
		ONR				
	...	...				
		...				
	Placebo (N=X)	None				
		ONR				

**Table 191: Laboratory Results by Severity, Time Point, and Treatment Group for Participants in the Safety Population Enrolled Prior to Protocol v11.0 – Ketones (continued)**

Time Point	Treatment Group	Baseline Severity	Post-Baseline Severity			
			Within Normal Range		Outside Normal Range	
			n	%	n	%
Notes: The “Max Post Baseline” rows indicate the maximum severity experienced by each participant at any time point post baseline, including unscheduled assessments. N = Number of participants in the Safety Population enrolled prior to Protocol v11.0 with non-missing results at the given time point. ONR = Outside of Normal Range.						

**Table 192: Laboratory Results by Severity, Time Point, and Treatment Group for Participants in the Safety Population Enrolled Under Protocol v11.0 – Ketones**

[Implementation Note: Repeat for the following treatment groups: All Participants, SAR440894 0.3 mg/kg, SAR440894 1 mg/kg, SAR440894 3 mg/kg, SAR440894 10 mg/kg, SAR440894 20 mg/kg, Placebo.

The table will include the following time points: Baseline, Day 2, Day 3, Day 4, Day 7, Day 14, Day 28, Day 56, Day 84, Day 112, Final Visit (Day 150), Max Severity Post Baseline.]

Time Point	Treatment Group	Baseline Severity	Post-Baseline Severity			
			Within Normal Range		Outside Normal Range	
			n	%	n	%
Day 2	All Participants (N=X)	None	x	xx	x	xx
		ONR				
	SAR440894 0.3 mg/kg (N=X)	None				
		ONR				
	...	...				
		...				
	Placebo (N=X)	None				
		ONR				
...	...	...				
Max Severity Post Baseline	All Participants (N=X)	None				
		ONR				
	SAR440894 0.3 mg/kg (N=X)	None				
		ONR				
	...	...				
		...				
	Placebo (N=X)	None				
		ONR				

**Table 192: Laboratory Results by Severity, Time Point, and Treatment Group for Participants in the Safety Population Enrolled Under Protocol v11.0 – Ketones (continued)**

Time Point	Treatment Group	Baseline Severity	Post-Baseline Severity			
			Within Normal Range		Outside Normal Range	
			n	%	n	%
Notes: The “Max Post Baseline” rows indicate the maximum severity experienced by each participant at any time point post baseline, including unscheduled assessments. N = Number of participants in the Safety Population enrolled under Protocol v11.0 with non-missing results at the given time point. ONR = Outside of Normal Range.						

**Tables with Similar Format:****Table 193: Laboratory Results by Severity, Time Point, and Treatment Group for Participants in the Safety Population Enrolled Prior to Protocol v11.0 – Leukocyte Esterase**

[Implementation Note: This table will have similar format to Table 191.]

**Table 194: Laboratory Results by Severity, Time Point, and Treatment Group for Participants in the Safety Population Enrolled Under Protocol v11.0 – Leukocyte Esterase**

[Implementation Note: This table will have similar format to Table 192.]

**Table 195: Laboratory Summary Statistics by Time Point and Treatment Group for the Safety Population – Urine WBC (wbc/hpf)**

[Implementation Note: Repeat for the following treatment groups: SAR440894 0.3 mg/kg, SAR440894 1 mg/kg, SAR440894 3 mg/kg, SAR440894 10 mg/kg, SAR440894 20 mg/kg, Placebo.]

The table will include the following time points: Baseline, Day 2, Day 3, Day 4, Day 7, Day 14, Day 28, Day 56, Day 84, Day 112, Final Visit (Day 150).]

Time Point	Treatment Group	Value at Visit					Change from Baseline				
		n	Mean	SD	Median	Min, Max	n	Mean	SD	Median	Min, Max
Baseline	SAR440894 0.3 mg/kg (N = X)	x	xx.x	xx.x	xx.x	xx.x, xx.x	-	-	-	-	-
	...						-	-	-	-	-
	Placebo (N = X)						-	-	-	-	-
Day 2	SAR440894 0.3 mg/kg (N = X)						x	xx.x	xx.x	xx.x	xx.x, xx.x
	...										
	Placebo (N = X)										
...	...										

Notes: N = Number of participants in the Safety population. n = Number of participants with a non-missing lab value at the respective visit. For the change from baseline, n represents the number of participants with non-missing values at baseline and the respective visit. SD = Standard Deviation. Min = Minimum. Max = Maximum.

**Tables with Similar Format:****Table 196: Laboratory Summary Statistics by Time Point and Treatment Group for the Safety Population – Urine RBC (rbc/hpf)****Table 197: Laboratory Summary Statistics by Time Point and Treatment Group for the Safety Population – Urobilinogen (mg/dL)**

[Implementation Note: Generate one table for each chemistry parameter. For calculated fields (Mean, SD, Median), decimal place should be the format in which the data were collected + 1 extra place. For Min, Max, decimal place should be in the same format in which the data were collected.]

[Repeat for each Chemistry Laboratory Parameter, number each table separately]

**Table 198: Clinically Significant Graded Urinalysis Results by Maximum Severity Post-Baseline, Parameter, and Treatment Group for Participants in the Safety Population Enrolled Prior to Protocol v11.0**

[Implementation Note: Repeat for the following treatment groups: All Participants, SAR440894 0.3 mg/kg, SAR440894 1 mg/kg, SAR440894 3 mg/kg, SAR440894 10 mg/kg, SAR440894 20 mg/kg, and Placebo.

The table will include the following parameters: Urine Protein, Urine Glucose, Bilirubin, Nitrite, Occult Blood, Urine WBC, Urine RBC, and Urobilinogen.]

Parameter	Treatment Group	N	Mild / Grade 1		Moderate/ Grade 2		Severe/ Grade 3	
			n	%	n	%	n	%
Urine Protein	All Participants	x	x	xx	x	xx	x	xx
	SAR440894 0.3 mg/kg							
	...							
	Placebo							
Urine Glucose	All Participants							
	SAR440894 0.3 mg/kg							
	...							
	Placebo							
Bilirubin	All Participants							
	SAR440894 0.3 mg/kg							
	...							
	Placebo							
...	...							

Notes: Participants are counted once per maximum severity among all clinically significant labs experienced at any time point post baseline, including unscheduled assessments. N = Number of participants in the Safety Population enrolled prior to Protocol v11.0 with available results post-baseline.

**Table 199: Clinically Significant Graded Urinalysis Results by Maximum Severity Post-Baseline, Parameter, and Treatment Group for Participants in the Safety Population Enrolled Under Protocol v11.0**

[Implementation Note: Repeat for the following treatment groups: All Participants, SAR440894 0.3 mg/kg, SAR440894 1 mg/kg, SAR440894 3 mg/kg, SAR440894 10 mg/kg, SAR440894 20 mg/kg, and Placebo.]

The table will include the following parameters: Urine Protein, Urine Glucose, Bilirubin, Nitrite, Occult Blood, Urine WBC, Urine RBC, and Urobilinogen.]

Parameter	Treatment Group	N	Mild / Grade 1		Moderate/ Grade 2		Severe/ Grade 3		Life-threatening/ Grade 4		Death/ Grade 5	
			n	%	n	%	n	%	n	%	n	%
Urine Protein	All Participants	x	x	xx	x	xx	x	xx	x	xx	x	xx
	SAR440894 0.3 mg/kg											
	...											
	Placebo											
Urine Glucose	All Participants											
	SAR440894 0.3 mg/kg											
	...											
	Placebo											
Bilirubin	All Participants											
	SAR440894 0.3 mg/kg											
	...											
	Placebo											
...	...											

Notes: Participants are counted once per maximum severity among all clinically significant labs experienced at any time point post baseline, including unscheduled assessments. N = Number of participants in the Safety Population enrolled under Protocol v11.0 with available results post-baseline.

**Table 200: Other Clinically Significant Abnormal Urinalysis Results by Maximum Severity Post-Baseline, Parameter, and Treatment Group for Participants in the Safety Population Enrolled Prior to Protocol v11.0**

[Implementation Note: Repeat for the following treatment groups: All Participants, SAR440894 0.3 mg/kg, SAR440894 1 mg/kg, SAR440894 3 mg/kg, SAR440894 10 mg/kg, SAR440894 20 mg/kg, and Placebo.

The table will include the following parameters: Ketones and Leukocyte Esterase.]

Parameter	Treatment Group	N	Within Normal Range		Outside Normal Range	
			n	%	n	%
Ketones	All Participants	x	x	xx	x	xx
	SAR440894 0.3 mg/kg					
	...					
	Placebo					
Leukocyte Esterase	All Participants					
	SAR440894 0.3 mg/kg					
	...					
	Placebo					

Notes: Participants are counted once per maximum severity experienced at any time point post baseline, including unscheduled assessments. N = Number of participants in the Safety Population enrolled prior to Protocol v11.0 with available results post-baseline.

**Table 201: Other Clinically Significant Abnormal Urinalysis Results by Maximum Severity Post-Baseline, Parameter, and Treatment Group for Participants in the Safety Population Enrolled Under Protocol v11.0**

[Implementation Note: Repeat for the following treatment groups: All Participants, SAR440894 0.3 mg/kg, SAR440894 1 mg/kg, SAR440894 3 mg/kg, SAR440894 10 mg/kg, SAR440894 20 mg/kg, and Placebo.

The table will include the following parameters: Ketones.]

Parameter	Treatment Group	N	Within Normal Range		Outside Normal Range	
			n	%	n	%
Ketones	All Participants	x	x	xx	x	xx
	SAR440894 0.3 mg/kg					
	...					
	Placebo					
Leukocyte Esterase	All Participants					
	SAR440894 0.3 mg/kg					
	...					
	Placebo					

Notes: Participants are counted once per maximum severity among all clinically significant labs experienced at any time point post baseline, including unscheduled assessments. N = Number of participants in the Safety Population enrolled under Protocol v11.0 with available results post-baseline.

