## 9.6. Clinical Laboratory Evaluations

Descriptive statistics for clinical laboratory test results including changes from baseline will be presented by time point and treatment group. Baseline is defined in [Section 3.3](#). Laboratory results obtained after start of dosing will be graded according to toxicity grading criteria given in [Table 5](#) and [Table 6](#) for participants who screened and enrolled prior to Protocol v11.0 and according to NCI CTCAE, Version 5.0 – November 2017 for participants who screen and enroll with Protocol v11.0. Note there are two instances in which the NCI CTCAE, Version 5.0 will not be used as implied: (1) eGFR toxicity will be assessed via chronic kidney disease, not acute kidney injury; and (2) calcium (corrected for albumin) will not be used and general grading (CTCAE term Investigations - Other) will be used instead. Laboratory results will be summarized by toxicity grade separately for participants who enrolled prior to Protocol v11.0 and participants who enrolled under Protocol v11.0.

Laboratory results that meet grading criteria per the toxicity table but fall within the specific site's reference range may be recorded in the database as normal and will only be reported as an AE if deemed related or clinically significant per the site PI. Any laboratory results that meet this criteria will be described in the CSR.

All safety laboratory results, change from baseline, and severity with applicable references ranges will be listed for each parameter by treatment group and time point. Unscheduled clinical laboratory evaluations will be included in listings of all clinical laboratory results but excluded from tabular and graphical summaries by time point, except when calculating the maximum severity post baseline. Abnormal laboratory results will also be presented. Abnormal laboratory results that do not have toxicity grading ranges defined will not have severity indicated in tables and listings except as “ONR” (outside of normal range). Abnormal laboratory results for parameters with defined toxicity grading ranges that are outside of the normal range but not at least mild in severity will have ONR as the severity included after the result.

The sort order for chemistry parameters will be as follows: sodium, potassium, bicarbonate, glucose, blood urea nitrogen, creatinine, eGFR, calcium, albumin, total protein, AP, AST, ALT, direct bilirubin, total bilirubin, and cystatin-C.

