## Urinalysis

- Proportions of participants with mild, moderate, and severe results for any urinalysis parameter will be presented for participants who enrolled prior to Protocol v11.0 in **Table 173** by treatment group, severity at baseline, time point, and maximum severity across all graded chemistry parameters. Proportions of participants with results that are mild, moderate, severe, life-threatening, or result in death for any urinalysis parameter will be presented for participants who enrolled under Protocol v11.0 in **Table 174** by treatment group, severity at baseline, time point, and maximum severity across all graded chemistry parameters.
- Proportions of participants with graded abnormal results will be presented by treatment group, severity at baseline, time point, and severity separately for participants enrolled prior to Protocol v11.0 and for participants enrolled under Protocol v11.0 for urinalysis parameters beginning in **Table 175** through **Table 190**. The proportions of participants with ONR results will be presented by treatment group, severity at baseline, time point, and severity for urinalysis parameters that do not have toxicity grading ranges defined in **Table 191** through **Table 194**.
- Proportions of participants with graded CS urinalysis results post-baseline will be presented by parameter, treatment group, and maximum severity of all CS results post-baseline for participants enrolled prior to Protocol v11.0 in **Table 198** and for participants enrolled under Protocol v11.0 in **Table 199**. The proportions of participants with CS ONR urinalysis results post-baseline will also be presented by parameter, treatment group, and maximum severity of all CS results for parameters that do not have toxicity grading ranges defined in **Table 200** for participants enrolled prior to Protocol v11.0 and in **Table 201** for participants enrolled under Protocol v11.0.

Descriptive statistics for each continuous laboratory parameter and its change from baseline, including mean, SD, median, min, and max, will be presented together for all participants by treatment group and planned time point.

- Descriptive statistics for each continuous chemistry parameter and its change from baseline will be presented by treatment group and planned time point in **Table 104** through **Table 119**.

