Blood (microscopic)—red blood cells per high power field (rbc/hpf)	0 – 3	HI	4 - 10	11 - 50	> 50 and/or gross blood
WBC (microscopic)—white blood cells per high power field (wbc/hpf)	0 – 5	HI	6 - 10	11 - 50	> 50 and/or gross blood
Urobilinogen (mg/dL)	0.2 – 1.0	HI	> ULN – 1.5	1.6 – 2.0	> 2.0
Vital Signs					
Fever (°C) g		HI	38.0 - 38.4	38.5 - 38.9	> 38.9
Fever (°F) g		HI	100.4 - 101.1	101.2 - 102.0	> 102.0
Tachycardia—beats per minute		HI	101 - 115	116 - 130	> 130 or ventricular dysrhythmias

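### The pre-v11.0 grading scale lets visible blood alone make urine WBC Grade 3, whatever the white-cell count

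*SAP*

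**What the plan says.** The defect sits in the grading scale, and the output tables inherit it.

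- **Scale.** SAP Table 5 has a row "WBC (microscopic)—white blood cells per high power field (wbc/hpf") with normal range 0-5, Grade 1 at 6-10, Grade 2 at 11-50, and Grade 3 given as "> 50 and/or gross blood". The row just above it, "Blood (microscopic)—red blood cells per high power field (rbc/hpf"), has the same Grade 3 cell. Protocol Appendix C (the source of Table 5) and Appendix D (the source of SAP Table 6) show the same wording in both rows. In the text I worked from, the Grade 3 column is missing from the urine part of SAP Table 6, so that cell has to be checked in the SAP itself.
- **Rule that applies it.** SAP section 9.6: "Laboratory results obtained after start of dosing will be graded according to toxicity grading criteria given in" Tables 5 and 6 for participants who screened and enrolled before Protocol v11.0. Later participants are graded by CTCAE v5.0.
- **Outputs.** The Table 185 shell, "Laboratory Results by Severity, Time Point, and Treatment Group for Participants in the Safety Population Enrolled Prior to Protocol v11.0 – Urine WBC", carries no cut-points of its own. Table 198 reports graded clinically significant urinalysis results, and its shell lists "Nitrite, Occult Blood, Urine WBC, Urine RBC, and Urobilinogen" among the parameters. Section 9.6 describes that table's content: "Proportions of participants with graded CS urinalysis results post-baseline will be presented by parameter, treatment group, and maximum severity of all CS results post-baseline".

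**The concern.** Gross blood is a statement about bleeding. It does not measure white cells, yet the and/or makes it sufficient by itself for Grade 3 on the white-cell row. A participant whose white-cell count is normal can therefore be placed in the severe column for urine WBC because of visible blood, and the same sample is already severe on the red-cell row.

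The stake is the readability of one descriptive safety parameter. Protocol section 2.1 relies on blood and urine markers to follow up the renal findings in mice. Protocol section 2.3.1 reports more hematuria/hemoglobinuria in male monkeys at the top dose. Bleeding and white cells should be separable in the urinalysis tables, and this cell merges them. Visible blood is also foreseeable for unrelated reasons: women are enrolled, and a footnote to Protocol Table 7-1 provides for urine abnormalities during menses. That footnote keeps such abnormalities out of the adverse events, but SAP section 9.6 does not take the samples out of the severity tables.

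**Working it through.** The plan gives no figure to reproduce, so the check is to apply the written cut-points to a sample and follow it through the tables.

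**1. The two rows side by side** (SAP Table 5; Protocol Appendices C and D agree)

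| Row | Normal | Grade 1 | Grade 2 | Grade 3: count | Grade 3: alternative |
|---|---|---|---|---|---|
| Urine RBC (rbc/hpf) | 0-3 | 4-10 | 11-50 | > 50 | gross blood |
| Urine WBC (wbc/hpf) | 0-5 | 6-10 | 11-50 | > 50 | gross blood |

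The counts differ between the rows at the low end. The Grade 3 cell is the same in both.

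**2. A sample with 3 wbc/hpf and visible blood, participant enrolled before v11.0**

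- By count, 3 lies in 0-5, so urine WBC is normal.
- By the rule as written, the gross-blood alternative is met, so urine WBC is Grade 3.
- On the red-cell row the same sample is Grade 3 through that row's own gross-blood term.

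**3. Where the sample appears**

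- Table 185 (urine WBC): Grade 3 on a literal reading.
- Table 187 (urine RBC): Grade 3, correctly.
- Table 198 (clinically significant graded results): urine WBC Grade 3 only if the investigator judged that result clinically significant.
- Table 173 (any urinalysis parameter): no change, because the red-cell row already gives Grade 3.
- Tables 186 and 199 (enrolled under v11.0): not affected, because they use CTCAE.
- Table 195 (summary statistics of urine WBC): not affected, because it summarises the count.

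**4. Size of one misgraded participant**

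- Full active dose group: 1/6 = 16.7%, about 17%.
- Full pooled placebo group: 1/10 = 10%.

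The Table 185 denominators are participants enrolled before v11.0 with a result at the time point. The documents do not give them. They can only equal or fall below 6 and 10, so the percentage could be higher.

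**5. The same sample with gross blood removed from the white-cell row only**

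Urine WBC at 3 wbc/hpf is not graded. Urine RBC is still Grade 3, so the bleeding remains visible in Tables 173 and 187.

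**The case against.** The best defence is that the error may never occur. SAP section 4.5.1 lists the urinalysis parameters, and there is no gross-blood or appearance variable among them. Urine WBC is held as a count, and a program that compares it with 5, 10 and 50 cannot reach the gross-blood alternative. This stands as a reason to expect little or no effect in practice. It does not settle the matter, because the SAP never says that urine WBC is graded on the count alone. Two programmers following Table 5 could give the same sample no grade or Grade 3.

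Section 9.6 also says that a result meeting a grade but lying inside the site's reference range may be recorded as normal. A count of 0-5 with visible blood would fit. The wording is permissive, so it softens the problem without removing it. The clinical-significance filter does protect Table 198, but not Table 185. Listing 18 shows each result with its reference range, so a careful reader could spot a misgraded value.

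Several stronger readings are tempting, and the documents do not support them:

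- A reader might infer that normal counts **will** be reported as severe. That is the literal result of the scale, but whether it happens depends on programming that the documents do not describe.
- A reader might try to estimate how many results are affected from menstruating participants. The number of women enrolled before v11.0, the share of urines with visible blood and the white-cell counts in those urines are not given.
- A reader might see a false signal of renal inflammation. The protocol speaks of blood and urine markers in general and names cystatin-C as the renal injury biomarker. It does not single out urine white cells.
- A reader might conclude that the cell was copied in error from the red-cell row. The identical wording suggests it, but the documents do not say so.

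**Conclusion.** The grading rule is wrong as written, and its impact is minor. For participants enrolled before v11.0, SAP Table 5 and Protocol Appendices C and D make gross blood sufficient for Grade 3 urine WBC at any white-cell count, and section 9.6 applies that scale to Table 185. Table 198 is exposed only for results judged clinically significant.

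The conclusion rests on reading the and/or literally and on the absence of any SAP statement that restricts urine WBC grading to the count. How many results would be affected cannot be estimated from the documents. The only size that can be stated is per participant: 17% of a full active group, 10% of a full pooled placebo group, and more if the pre-v11.0 denominators are smaller. It concerns one parameter in a descriptive safety analysis.

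**What to change.** Do one of the following before the tables are programmed:

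- delete the gross-blood alternative from the Grade 3 cell of the urine WBC row in SAP Table 5, and in Table 6 if it appears there; or
- add one sentence to SAP section 9.6 stating that urine WBC is graded on wbc/hpf only.

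Leave gross blood in the red-cell row. Record the difference from Protocol Appendices C and D in SAP section 15 or in a note to file; a retrospective protocol amendment is not needed.

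The cost is at most two table cells or one sentence, plus the note. Grades can be rederived from the stored counts, and no information is lost because the red-cell row still captures visible bleeding.
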